## 1. STUDY OBJECTIVES

Primary objective: To evaluate the acute success of pulmonary vein isolation (PVI) using pulsed field ablation (PFA) guided by the CARTO SOUND™ FAM system in patients with paroxysmal atrial fibrillation (AF).

Secondary objectives: (1) 30-day safety (serious adverse events related to the system/procedure); (2) procedure efficiency metrics (total procedure time, mapping time, ablation time, fluoroscopy time); (3) catheter contact quality; (4) tissue proximity indicator (TPI) performance.

## 2. STUDY DESIGN

Prospective, multicenter, single-arm, feasibility study.

Sample size: 70 participants.

Enrollment period: 11 months; Follow-up: 1 month post-procedure.

## 3. ELIGIBILITY CRITERIA

Inclusion:

- Diagnosis of paroxysmal AF with indication for catheter ablation.

- Age 18-80 years.
- Signed informed consent.
- Willing to comply with all study visits and assessments.

Exclusion:

- Valvular AF, untreated thyroid disease, acute coronary syndrome, or AF secondary to cardiomyopathy.
- Contraindications to catheter ablation (e.g., left atrial thrombus, coagulopathy, severe organ dysfunction).
- Pregnancy or breastfeeding.
- BMI >40 kg/m^2 or severe sleep apnea.
- Participation in another clinical trial.
- Any contraindication to study devices per instructions for use.

#### 4. INTERVENTION

All participants undergo PVI using the Varipulse™ PFA catheter under the guidance of the CARTO SOUND™ FAM system. The system uses intracardiac echocardiography (ICE) and an AI algorithm to reconstruct a 3D model of the left atrium and pulmonary veins. The VIZIGO™ steerable sheath may be used.

#### 5. OUTCOME MEASURES

Primary endpoint (acute success):

Composite endpoint requiring all of the following:

- (1) successful left atrial model construction using the study catheter;
- (2) electrical isolation of all target pulmonary veins (entry block confirmed);
- (3) completion of ablation using only study devices (no cross-over to other tools).

Secondary endpoints:

- (1) Incidence of 30-day serious adverse events (SAEs) related to CARTO SOUND™ FAM or PFA procedure.
- (2) Total procedure time; mapping time; ablation time; fluoroscopy time.
- (3) Catheter contact quality assessed by ICE.
- (4) Percentage of positive tissue proximity indicator (TPI) sites.

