## 6. STATISTICAL PLAN

Descriptive statistics will be used. The primary endpoint will be reported as frequency with exact 95% confidence interval. Continuous variables will be expressed as mean±SD or median (IQR). For mapping time, comparison with historical data (4.5±1.0 min) will be performed using one-sample t-test or Wilcoxon test. SAE incidence will be calculated with exact binomial 95% CI. Subgroup analyses (by site, operator experience)

and exploratory logistic regression may be performed. Significance level:  $\alpha=0.05$  (two-sided). Software: R version 4.3.

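### The only 30-day safety endpoint counts SAEs judged related, with no all-cause rate beside it, and Section 6 words the numerator without that restriction

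*Protocol*

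**What the plan says.** Three places in the protocol describe the safety measure.

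- Section 1 (Study Objectives), first secondary objective: "30-day safety (serious adverse events related to the system/procedure".
- Section 5 (Outcome Measures), secondary endpoint (1): "Incidence of 30-day serious adverse events (SAEs) related to CARTO SOUND™ FAM or PFA procedure".
- Section 6 (Statistical Plan): "SAE incidence will be calculated with exact binomial 95% CI".

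The first two restrict the count to related events. The third does not mention relatedness. No other safety endpoint appears in Section 5.

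The design context is in Sections 2 and 4: "Prospective, multicenter, single-arm, feasibility study"; "Sample size: 70 participants"; "Follow-up: 1 month post-procedure"; and "All participants undergo PVI using the Varipulse™ PFA catheter under the guidance of the CARTO SOUND™ FAM system".

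**The concern.** A relatedness filter makes the numerator depend on a causal judgement. With a single arm and one common treatment, whoever makes that judgement knows what the participant received, and there is no comparison group whose event rate could show an excess. That does not make the judgement wrong. It does mean that the one safety rate the protocol defines rests on it alone, because no count free of attribution is specified next to it.

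The wording in Section 6 adds a second, smaller problem. Someone following Section 5 would count related SAEs only, while someone following Section 6 literally could count all SAEs. The protocol does not say which proportion the exact interval belongs to.

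Safety is listed first among the secondary objectives, and in a study of this size the number of SAEs may be small. The classification of one or two participants could then visibly change the figure that readers take away.

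**Working it through.** The protocol gives no expected SAE rate, safety threshold or sample-size derivation, so there is no stated figure to reproduce. The steps below compare the wording and then illustrate scale using the protocol's own sample size and interval method.

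**Step 1. Wording compared.**

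| Place | Events counted |
|---|---|
| Section 1 | SAEs related to the system or procedure |
| Section 5, secondary endpoint (1) | SAEs related to the mapping system or the PFA procedure |
| Section 6 | SAEs, no relatedness condition stated |

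Sections 1 and 5 agree in substance. Section 6 neither repeats the restriction nor defines an all-cause analysis, so it is ambiguous.

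**Step 2. Effect of one reclassification.** With n = 70 (Section 2) and the participant as the unit, one participant changes the rate by 1/70 = 0.0143, or 1.4 percentage points.

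**Step 3. Exact intervals at n = 70.** The method is Clopper-Pearson. For k participants with an event, the lower limit is the 0.025 quantile of Beta(k, 70 − k + 1), taken as 0 when k = 0. The upper limit is the 0.975 quantile of Beta(k + 1, 70 − k).

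| k | Rate | Exact 95% interval |
|---|---|---|
| 0 | 0% | 0 to 5.1% |
| 1 | 1.4% | 0.04 to 7.7% |
| 2 | 2.9% | 0.35 to 9.9% |
| 3 | 4.3% | 0.9 to 12.0% |
| 4 | 5.7% | 1.6 to 14.0% |

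Moving one participant out of the numerator shifts the upper limit by about 2.0 to 2.6 points in this range (for example 9.9% to 7.7%, or 7.7% to 5.1%). Each interval takes k as given. It covers sampling error and carries no allowance for error in deciding who belongs in k.

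**Step 4. Sensitivity to the share attributed.** Let p be the true proportion of participants with a procedure-caused SAE, and s the share of those judged related. The expected reported rate is p·s, and the chance of reporting no related SAE is (1 − p·s)^70. Both p and s are assumptions made here, not protocol figures.

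| Assumed p | Assumed s | Reported rate | Chance of reporting zero |
|---|---|---|---|
| 3% | 100% | 3.0% | 0.970^70 = 11.9% |
| 3% | 80% | 2.4% | 0.976^70 = 18.3% |
| 3% | 50% | 1.5% | 0.985^70 = 34.7% |
| 5% | 100% | 5.0% | 0.950^70 = 2.8% |
| 5% | 80% | 4.0% | 0.960^70 = 5.7% |
| 5% | 50% | 2.5% | 0.975^70 = 17.0% |

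The table shows what under-attribution would do if it occurred. Nothing in the protocol indicates that it will.

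**The case against.** The best defence is that nothing in Section 5 is wrong in itself. Restricting to device- or procedure-related SAEs is a legitimate endpoint, and Section 1 matches it. Without a control arm, an all-cause rate cannot separate treatment harm from background illness either: each unrelated admission would add 1.4 points. The outcome is descriptive and secondary in a feasibility study, with no safety hypothesis or threshold, so no test result or sample size depends on it. An SAP that is not shown may also tabulate all SAEs.

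Most of this stands. It rules out replacing the related-SAE endpoint and keeps the point small. It does not answer why the related rate should be the only safety endpoint, or why Section 6 describes the numerator differently. The endpoint is fixed in the protocol, so the difference in wording is already present in the text at hand.

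A reader might also infer that complications from ICE or the sheath fall outside the filter. The text does not support that. Section 4 describes ICE as something the mapping system itself uses, and, although "The VIZIGO™ steerable sheath may be used" makes the sheath optional, vascular access and a sheath used during the intervention belong naturally to the PFA procedure. Such an event would be excluded only if someone judged it unrelated to the procedure as a whole, and nothing in the protocol directs that.

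**Conclusion.** The point holds as a modest improvement to a stated endpoint. The protocol's sole 30-day safety outcome depends entirely on attribution made with knowledge of treatment, and Section 6 leaves the numerator ambiguous. That the judgement is unblinded is inferred from the single-arm design, because the protocol neither uses the word nor names the assessor.

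The size is 1.4 percentage points per reclassified participant, assuming all 70 are in the denominator. Stronger readings are not supported:

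- A reader might conclude that attribution would roughly halve the upper confidence limit, from 9.9% to 5.1%. That requires two affected participants, both reclassified as unrelated, and the protocol gives no basis for expecting it.
- A reader might conclude that the reported rate is biased downwards. The documents show only that the rate is exposed to such error, not that the error is present or which way it runs.

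The primary endpoint, its analysis and the sample size are unaffected.

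**What to change.** 1. Keep secondary endpoint (1) as the related-SAE proportion.
2. Add a co-reported line: the proportion of participants with any SAE within 30 days of the procedure, irrespective of attribution, with its own exact 95% interval.
3. Align Sections 1, 5 and 6 so that each says whether it means related SAEs, all SAEs or both. In Section 6, name both proportions and state that each gets an exact interval.

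The cost is a few words in three sections and one extra table row. The 30-day window already fits the planned one-month follow-up, so no visit is added. If all SAEs are captured under the GCP commitment in Section 8, no new data are needed; that capture is inferred from the commitment, as the protocol does not spell it out. The downside is a second figure that may look less favourable and will include some background events, which is why it should stand beside the related rate and not replace it.

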## 6. STATISTICAL PLAN

Descriptive statistics will be used. The primary endpoint will be reported as frequency with exact 95% confidence interval. Continuous variables will be expressed as mean±SD or median (IQR). For mapping time, comparison with historical data (4.5±1.0 min) will be performed using one-sample t-test or Wilcoxon test. SAE incidence will be calculated with exact binomial 95% CI. Subgroup analyses (by site, operator experience)

and exploratory logistic regression may be performed. Significance level:  $\alpha=0.05$  (two-sided). Software: R version 4.3.

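### The one-sample test of mapping time against historical data ignores the sampling error of the historical mean, so two-sided 0.05 holds for the constant 4.5 min but not for the comparison described

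*Protocol*

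**What the plan says.** Section 2 describes a "Prospective, multicenter, single-arm, feasibility study" with "Sample size: 70 participants", so there is no concurrent control. Section 5 lists mapping time as one of four times within a single secondary endpoint: "Total procedure time; mapping time; ablation time; fluoroscopy time". Section 6 is otherwise mainly descriptive. For mapping time alone it commits to a test: "comparison with historical data (4.5±1.0 min) will be performed using one-sample t-test or Wilcoxon test". The significance level for the plan is two-sided 0.05. Subgroup analyses "and exploratory logistic regression may be performed", so these are optional, and the mapping-time comparison is the only hypothesis test the protocol commits to. The protocol gives neither the source of the 4.5±1.0 min nor the number of patients behind it, and nowhere calls 4.5 min a performance goal.

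**The concern.** A reference that is called historical data and given with an SD is a sample mean, and a sample mean has its own error. A one-sample test, parametric or rank-based, treats 4.5 as known exactly, and the SD of 1.0 enters neither calculation. The method named therefore does not match the comparison described: its standard error covers this trial's patients only.

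Because the study has one arm, this test is the only named route to a statement that mapping is faster, or slower, than in earlier practice. If the historical series was small, a significant result could reflect chance in the reference figure. The protocol has already fixed the type of test, so an analysis plan that follows it would carry the mismatch forward.

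**Working it through.** **Inputs.** From the protocol: n = 70 (Section 2); historical mean 4.5 min and SD 1.0 min, one-sample test, two-sided 0.05 (Section 6). Assumed: true SD 1.0 min in both series, equal true means, normal data, and a range for the historical sample size n_h, which the protocol does not state.

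**Step 1: reproduce the stated level.** With 4.5 as a constant, the t-test has 69 degrees of freedom and critical value 1.995. Its type I error is 2·P(T₆₉ > 1.995) = 0.0500, as stated. Its standard error is 1.0/√70 = 0.120 min, so it reaches p < 0.05 at 1.995 × 0.1195 = 0.238 min, about 14 seconds.

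**Step 2: let 4.5 be the mean of n_h patients.** The standard error of the comparison is 1.0 × √(1/70 + 1/n_h). The planned test uses 1.0/√70, which is too small by the factor √(1 + 70/n_h). Over repeats of both series, the actual level is

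2·P(T₆₉ > 1.995/√(1 + 70/n_h)).

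For n_h = 70 the factor is √2 = 1.414, 1.995/1.414 = 1.411, and the level is 0.163.

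In the table, the share of variance counted is n_h/(n_h + 70). The last column is 1.96 times the correct standard error; with the same multiplier the one-sample figure is 1.96 × 0.1195 = 0.234 min.

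| Historical n (assumed) | SE of comparison (min) | SE too small by factor | Actual two-sided level | Share of variance counted | Difference needed (min) |
|---|---|---|---|---|---|
| 30 | 0.218 | 1.83 | 27.8% | 30% | 0.428 |
| 70 | 0.169 | 1.41 | 16.3% | 50% | 0.331 |
| 100 | 0.156 | 1.30 | 13.1% | 59% | 0.305 |
| 200 | 0.139 | 1.16 | 9.1% | 74% | 0.272 |
| 500 | 0.128 | 1.07 | 6.6% | 88% | 0.250 |
| 1000 | 0.124 | 1.03 | 5.8% | 93% | 0.242 |
| 5000 | 0.120 | 1.01 | 5.2% | 99% | 0.236 |

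**Step 3: check by simulation.** For n_h = 30, 70 and 200 the one-sample t-test rejected a true null in 27.4%, 16.5% and 9.1% of 20,000 runs. The Wilcoxon signed-rank test rejected in 26.5%, 16.3% and 9.0% of 4,000 runs, so that option does not avoid the problem. A Welch two-sample test rejected in 4.9%, 5.3% and 5.1% of 20,000 runs.

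**Sensitivity to the equal-SD assumption.** If the SD is σ here and σ_h historically, the factor becomes √(1 + 70σ_h²/(n_h σ²)). A smaller SD in this trial makes the inflation larger, and a larger SD makes it smaller.

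**The case against.** The strongest reply is that a one-sample test answers its own question correctly. For the null that mean mapping time equals 4.5 min, the level is 0.05 to the last digit, and testing a single arm against a fixed reference is common practice. This stands, so a reader who infers that the stated level is simply wrong goes too far. It fails only for equality with the mean of the historical population. The reply would settle the matter had the protocol declared 4.5 min a fixed value; instead it presents historical data with an SD.

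A second reply concerns size. A reader might infer that false positives are far above 5%, or that the test captures only half of the uncertainty. The protocol supports neither as a general statement. The half is a share of variance and is exact only for a historical n of 70. With 500 or 1000 historical patients the level is 6.6% or 5.8%, which is a small excess. Nor is the missing historical n a fault in itself, since it may be given in an analysis plan not seen here.

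A third reply concerns consequence. The study is a feasibility study, and no sample size, success criterion or decision rule in the protocol rests on this p-value. This also stands and limits how serious the point is.

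Finally, a two-sample test repairs sampling error only. Differences between the historical patients, operators or sites and those of this trial remain whichever test is used.

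**Conclusion.** The concern holds in a limited form. The named test fits a constant of 4.5 min and does not fit the comparison with historical data that Section 6 describes. For that comparison the direction is certain: the actual level exceeds 5% for every finite historical sample. The size is not known from the protocol. Under SD 1.0 min in both series and 70 participants here, it runs from about 28% at a historical n of 30 down to 5.8% at 1000. Importance is moderate. One time measure within a secondary endpoint is affected; the primary endpoint and the serious adverse event incidence, both reported with exact intervals, are not. The documents do not support a claim that the trial's main conclusions are at risk.

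**What to change.** Change the mapping-time sentence in Section 6:

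- Replace the one-sample test with a Welch comparison from summary statistics: this trial's mean, SD and n against the historical mean of 4.5 min, SD of 1.0 min and its n. State the source and n of the historical series, and report the difference with its 95% confidence interval.
- Describe the result as a non-randomised comparison whose interval covers sampling error only.
- If times are clearly skewed, report this trial's median (IQR) beside the historical figure without a p-value. A rank test is a poor fallback because the reference is a mean: in 5,000 simulated lognormal samples with true mean 4.5 and SD 1.0, the Wilcoxon test against the constant 4.5 rejected in 7.5%.
- If the historical n cannot be obtained, either report this trial's mean with 95% confidence interval beside 4.5±1.0 min descriptively with no p-value, or declare 4.5 min a fixed benchmark, keep the one-sample test, and limit the conclusion to that value.

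The cost is a short rewording and, with the Welch comparison, a wider interval and less chance of a significant result: with a historical n of 70 the difference needed rises from about 0.24 to about 0.33 min. No change to sample size or data collection is needed.

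### A one-sample Wilcoxon test of mapping time against 4.5 min sets a pseudo-median against a historical mean, and rejects too often toward shorter times if mapping times are right-skewed

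*Protocol*

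**What the plan says.** Mapping time is one of the secondary efficiency endpoints in Protocol section 5 ("Total procedure time; mapping time; ablation time; fluoroscopy time"). The design in section 2 is "Prospective, multicenter, single-arm, feasibility study", with "Sample size: 70 participants", so there is no concurrent control.

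For this endpoint section 6 plans a test: "comparison with historical data (4.5±1.0 min) will be performed", and the method is given as "using one-sample t-test or Wilcoxon test". The significance level is 0.05, two-sided.

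Section 6 does not label 4.5±1.0, but the sentence just before it sets the notation: "Continuous variables will be expressed as mean±SD or median (IQR". The ± sign goes with a mean and SD, and medians are shown with an IQR. So 4.5 reads as a mean and 1.0 as an SD. No historical median, individual historical times or historical sample size is given.

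**The concern.** The two tests offered do not test the same thing. The t-test asks whether the mean differs from 4.5. The signed-rank test asks whether the distribution is centred symmetrically on 4.5, and what it responds to is the pseudo-median (the median of the average of two independent observations). For a symmetric distribution, mean and pseudo-median are equal and either test will do. For a right-skewed one the pseudo-median lies below the mean, so the Wilcoxon null hypothesis is false even when the new system's mean mapping time equals the historical mean.

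The usual reason for turning to a Wilcoxon test is that the data look skewed, and that is the situation in which its result against a mean is hardest to interpret. At stake is a p-value that could be read as evidence of shorter mapping when the mean has not changed. This is the only hypothesis test that section 6 ties to a named endpoint; the primary and safety endpoints are reported with confidence intervals.

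**Working it through.** The protocol gives no power or effect-size figure for mapping time, so there is nothing of its own to reproduce. The check is the type I error when the true mean equals the historical mean.

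**Inputs from the protocol:** reference value 4.5 min and SD 1.0 (section 6); two-sided alpha 0.05, hence 2.5% in each direction (section 6); n = 70 (section 2), assuming every participant has a mapping time.

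**Assumption:** the shape of the distribution, which the protocol does not give. Five shapes were used, all with mean 4.5 and SD 1.0.

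**Which Wilcoxon test.** A rank-sum test needs individual historical times. Section 6 gives only a summary, so as written the option can only be a signed-rank test of the differences from 4.5.

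**How far the pseudo-median lies from 4.5**

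- Gamma: shape (4.5/1.0)² = 20.25, skewness 2/√20.25 = 0.44; pseudo-median 4.464, a shift of 0.036 min (about 2 s).
- Lognormal: log-variance ln(1 + (1.0/4.5)²) = 0.0482, median 4.5·exp(−0.0482/2) = 4.393, skewness 0.68; pseudo-median 4.446, a shift of 0.054 min (about 3 s).
- Shifted exponential (3.5 plus an exponential with mean 1.0): median 3.5 + ln 2 = 4.193, skewness 2.0; pseudo-median 4.339, a shift of 0.161 min (about 10 s).

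**Rough hand check.** The standard error of a mean at n = 70 is 1.0/√70 = 0.1195. Taking this as the scale, the chance of rejecting toward shorter times is about Φ(−1.96 + shift/0.1195):

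- Gamma: Φ(−1.96 + 0.30) = Φ(−1.66) ≈ 4.9%
- Lognormal: Φ(−1.96 + 0.45) = Φ(−1.51) ≈ 6.6%
- Shifted exponential: Φ(−1.96 + 1.35) = Φ(−0.61) ≈ 27%

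**Simulation** (20,000 trials per shape; signed-rank test by normal approximation with continuity correction; t-test on 69 df; simulation standard error √(0.05·0.95/20,000) = 0.15 percentage points at a 5% rate):

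| Shape (mean 4.5, SD 1.0) | Wilcoxon: shorter | Wilcoxon: longer | Wilcoxon: total | t-test: shorter | t-test: total |
|---|---|---|---|---|---|
| Nominal | 2.5% | 2.5% | 5% | 2.5% | 5% |
| Normal | 2.6% | 2.5% | 5.1% | 2.6% | 5.1% |
| Gamma | 4.8% | 1.3% | 6.1% | 2.8% | 5.0% |
| Lognormal | 6.9% | 0.7% | 7.6% | 3.4% | 5.2% |
| Shifted exponential | 28.7% | 0.0% | 28.7% | 5.0% | 6.1% |
| Left-skewed mirror image | 0.1% | 29.1% | 29.1% | 1.1% | 6.2% |

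A repeat simulation of the three right-skewed shapes gave 4.4%, 6.7% and 29.1% toward shorter times for the Wilcoxon test, and 2.7%, 3.3% and 5.0% for the t-test. The normal row shows that the simulation is calibrated, so the excess comes from skewness.

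**Would a normality pre-test cure it?** In a separate run of 8,000 lognormal trials at SD 1.0, total rejections were 7.2% when the Wilcoxon test was always used and 6.8% when a Shapiro-Wilk test chose between the two. The pre-test sends the skewed samples to the mismatched test.

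**The case against.** The strongest reply has four parts.

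*The choice between the tests belongs to the SAP.* This stands as far as it goes. Only the protocol is at hand, and an SAP may state when each test applies. A reader might infer that the sponsor is free to choose after seeing the data; the protocol alone does not show that, and it is not part of this point. What remains is that the protocol itself permits a Wilcoxon test against a value reported as a mean, and a selection rule based on normality would leave the mismatch in place.

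*The effect is modest at the stated SD.* This stands for mild skewness. With a gamma or lognormal shape the pseudo-median shifts by 2 to 3 seconds and the total error is 6.1 to 7.6%. Total errors of about 11% and 15% arise for a lognormal with SD 1.5 or 2.0, but the protocol gives neither of those SDs. The shifted exponential shows that a large error is possible at SD 1.0, but only with strong skewness.

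*The t-test tilts the same way.* It does: 2.8 to 5.0% toward shorter times in the right-skewed cases, against 2.5%. The tilt is much smaller, and the total stays at 5.0 to 6.1%.

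*Another feature of the same comparison may matter more.* Treating 4.5 as a known constant ignores its own sampling error. If, as an assumption, it came from 70 patients with the same SD, the two-sided error for normal data would be 2·(1 − Φ(1.96/√2)) ≈ 17%. That is a separate matter affecting both tests, and it does not make the Wilcoxon option appropriate.

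**Conclusion.** The point holds conditionally. If mapping times are right-skewed, the Wilcoxon option in section 6 rejects toward shorter times too often when the true mean is exactly 4.5 min: about 4 to 5% (gamma), 7% (lognormal) and 29% (shifted exponential) against 2.5%, at n = 70 and SD 1.0. The one-sample t-test gives about 3 to 5% in the same cases.

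This rests on reading 4.5 as a mean, which follows from the protocol's notation but is not labelled, and on the assumed shapes. A reader might infer that the test always favours the new system. The documents do not support that: nothing is said about the shape of mapping times, normal data show no excess, and left skew reverses the bias. Nor does the protocol state a hypothesis of faster mapping; the test is two-sided and no direction is named.

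Mapping time is a secondary endpoint in a feasibility study, so the primary result is untouched. The change is still worth making before the study starts, because it costs almost nothing.

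**What to change.** In Protocol section 6, delete the Wilcoxon alternative and make the one-sample t-test on the mean the comparison with 4.5 min. Add a bootstrap confidence interval for the mean as a sensitivity analysis for skewness, and report median and IQR descriptively.

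Keep a Wilcoxon test only if the matching historical data can be obtained: a historical median for a one-sample test, or individual historical times for a two-sample test. A Welch-type comparison is not available from the protocol as it stands, because it needs the historical sample size.

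The cost is a short wording change, with no added data and no burden on participants. The small downside is some loss of efficiency compared with a rank test if the times are heavy-tailed.
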